Adolescent Health Club Component and Evaluation: Households with AGYW ages 15 to 25 will be identified by community health workers from randomly selected block sectors of the study area. Clubs will be conducted in separate neighborhood sectors, to limit contamination. Conducting club meetings near to the lanes adolescent girls live in will make it easier for them to attend. To further assess and address potential contamination, we will ask individuals to verify the adolescent health club they attended in the post-intervention survey, whether they attended an additional health club outside our intervention (such as, in school). If any contamination is evident based on this question, then we will model it. AGYW and their mothers (if unmarried and under the age of 18) will be approached by a member of the research team and the adolescent health club intervention will be explained. If consent is obtained, the AGYW will be enrolled, and randomized to either participate or join the wait-list. AGYW will complete the pre-intervention evaluation instrument upon enrollment. In addition to the activities in the "It's All One" Curriculum spread over eight modules, providers from the sensitization component will attend one meeting to discuss services available in the adolescent-friendly clinics, and hear young women's previous experiences accessing care. Similar to the process for the provider sensitization component, the facilitator will complete a log after each session to code activities as implemented fully, implemented partially or modified significantly and describe any changes. The log will also include a section to document any unusual events associated with any of the sessions, and the effect of these events on implementation, acceptability, or feasibility. Every other session will be observed and documented in fieldnotes that will be analyzed to contribute to process evaluation (see analysis details below). As with the provider component, the log and fieldnotes will enable a qualitative assessment of intervention fidelity. When young women complete the curriculum, they will also complete the post-intervention evaluation instrument. A sub-sample of young women (N=15) will be asked to participate in a focus group discussion to reflect on the club's impact and acceptability. Domains measured by previously validated instruments^(32, 48, 66, 123-126) to be covered in the pre- and post-intervention surveys are shown in Table 3. There are relatively few validated quantitative measures of implementation outcomes,^(127, 128) and none in Hindi, thus the measure we have chosen⁽¹²⁹⁾ will have to be translated and back-translated to ensure comprehension.

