Qualitative analysis: The observations and interviews conducted during and after the intervention will be transcribed, translated into English (as needed), and entered into the qualitative software analysis program Atlas.ti (v.8.1).⁽¹¹²⁾ A modified framework approach^(113, 115, 134) to coding will be used in which deductive themes will be developed *a priori* based on the study's conceptual framework and implementation indicators, and inductive codes will be developed and applied iteratively based on review of the transcribed documents. Text will then be reviewed for patterns of consistency, variation, relationships between themes and exemplary cases or quotations. Qualitative data will also be merged with the quantitative findings to triangulate results and further contextualize the quantitative indicators, in keeping with a parallel mixed methods design.^(114, 116, 135)

Quantitative analysis: I will use R to analyze the data. Descriptive statistics will be obtained for continuous and categorical variables. The health outcome scales to be used in this study are well-validated (in contrast to the implementation outcome scales), and can be assumed to have approximate normal distributions, although these assumptions will be checked. This study will conduct both within and between-group analyses for the adolescent club component. All subjects will have pre- and post-treatment within-subject measures, and these comparisons can be preliminarily analyzed with paired t-tests. Primary analyses will focus on using repeated measures general linear mixed models to examine comparisons across recruitment cohorts. We will also be able to compare the treated participants from group 1 with the untreated participants in group 2, followed by the group 2 treated participants with the untreated group 3 participants, and finally the group 3 treated participants with the untreated group 4 participants, and can use repeated general linear mixed models for this unbalanced design.

5. Genetic Testing N/A

A. Describe

- i. the types of future research to be conducted using the materials, specifying if immortalization of cell lines, whole exome or genome sequencing, genome wide association studies, or animal studies are planned *Write here*
- ii. the plan for the collection of material or the conditions under which material will be received *Write here*
- iii. the types of information about the donor/individual contributors that will be entered into a database *Write here*

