For the provider/staff sensitization component, a total of N=60 providers and staff will be recruited from the public and private clinics where AGYW were recruited for the formative quantitative survey. There will be two separate groups of 20 people each who undergo the sensitization workshop. The workshop will take place over four days. In previous work in the study area, retaining providers for a short intervention such as the one described in this proposal has not been a challenge and therefore we anticipate no challenges in recruiting the required sample size.

For the adolescent health club component, households with AGYW between the ages of 15 and 25 will be identified by Apnalaya's field team from randomly selected block sectors of the study area. AGYW and their mothers (if unmarried and under the age of 18) will be approached by a member of the research team and the adolescent health club intervention will be explained. If consent is obtained, the AGYW will be enrolled to either participate in the health club immediately or join the wait-list. An initial sample of 50 AGYW will be recruited (one group of 25 to begin intervention immediately, and one wait-list group). After the first intervention group has completed the health club curriculum, the wait-listed group will begin the intervention, and another 25 AGYW will be recruited for a wait-list. This will continue until four groups of 20-25 AGYW complete the health club intervention. Factoring in an attrition rate of 20%, the expected N at endpoint is 80. AGYW will complete the pre-intervention evaluation instrument upon enrollment. When young women complete the health club curriculum, they will also complete the post-intervention evaluation instrument. A sub-sample of young women will be asked

to participate in a focus group discussion to reflect on the club's impact and acceptability. To limit differences in

the time needed to assemble the health club groups, we will avoid recruiting during busy religious festivals/holidays (such as Ramadan) or vacation periods.

b. Describe how potential subjects are contacted.

Key informants and healthcare providers/staff for all phases will be contacted in the following ways: through in-person meetings, and snowball referrals/introductions via email (email recruitment template is attached) or cell phone.

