AGYW for the qualitative data collection will be contacted primarily through Apnalaya's outreach activities, and through snowball referrals/introductions either in person or through cell phone. For the quantitative portion of the formative research, a random sample of adolescent girls and young women (AGYW; ages 15-25 years old) seeking care at a set of public (N=3) and private (N=3) healthcare facilities in the study area will be referred by their healthcare provider/Apnalaya health promotion team member to me or my research assistant and asked to participate in a brief survey.

For the adolescent health club component, households with AGYW between the ages of 15 and 25 will be identified by Apnalaya's field team from randomly selected block sectors of the study area. AGYW and their mothers (if unmarried and under the age of 18) will be approached by a member of the research team and the adolescent health club intervention will be explained. If consent is obtained, the AGYW will be enrolled to either participate in the health club immediately or join the wait-list.

c. Who is recruiting potential subjects?

Subjects will be recruited by the 3-4 members of Apnalaya's adolescent outreach team.

4. Assessment of Current Health Provider Relationship for HIPAA Consideration:

Does the Investigator or any member of the research team have a direct existing clinical relationship with any potential subject?

Yes, all subjects

Yes, some of the subjects

No

If yes, describe the nature of this relationship.

None of the members of the research team will have a direct existing clinical relationship with any potential subjects, however, healthcare providers and Apnalaya staff may tell potential subjects about the study, and refer them to me or my research assistant.

5. Request for waiver of HIPAA authorization: (When requesting a waiver of HIPAA Authorization for either the entire study, or for recruitment purposes only. Note: if you are collecting PHI as part of a phone or email screen, you must request a HIPAA waiver for recruitment purposes.)

Choose one:

For entire study

For recruitment/screening purposes only

For inclusion of non-English speaking subject if short form is being used and there is no translated HIPAA research authorization form available on the University's HIPAA website at hipaa.yale.edu.

i. Describe why it would be impracticable to obtain the subject's authorization for use/disclosure of this data: *Write here*

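### The research plan says every enrolled woman is randomised to club or wait-list, but the recruitment sequence allows this for at most 50 of 100 women and one of the three between-group contrasts

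*Combined protocol and SAP*

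**What the plan says.** Section I, item 4 (Adolescent Health Club Component and Evaluation) says that, on consent, "the AGYW will be enrolled, and randomized to either participate or join the wait-list". It gives no method, ratio or unit of allocation. It also places clubs in separate neighbourhood sectors to limit contamination.

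Section III, items 3a and 3b describe the same step without the word randomised: "the AGYW will be enrolled to either participate in the health club immediately or join the wait-list". Item 3a then sets the sequence. It begins: "An initial sample of 50 AGYW will be recruited (one group of 25 to begin intervention immediately, and one wait-list group". When the first club finishes, group 2 starts and "another 25 AGYW will be recruited for a wait-list. This will continue until four groups of 20-25 AGYW complete the health club intervention".

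The Quantitative analysis paragraph of Section I, item 4 states: "Primary analyses will focus on using repeated measures general linear mixed models to examine comparisons across recruitment cohorts". It names three between-group contrasts: group 1 treated v group 2 untreated, "followed by the group 2 treated participants with the untreated group 3 participants", and then group 3 treated v group 4 untreated. It does not say which of these is randomised, or how recruitment wave or period enters the model.

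On survey timing, item 3a gives two points: "AGYW will complete the pre-intervention evaluation instrument upon enrollment" and "When young women complete the health club curriculum, they will also complete the post-intervention evaluation instrument". Figure 2, to which the Study Design paragraph refers for the wait-list design, is not shown in the text available.

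**The concern.** A woman can be randomised between club and wait-list only if both are open to her when she enrols. For groups 3 and 4 only the wait-list is open. The plan thus claims for everyone a property that half the women cannot have.

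This matters because the cross-cohort comparisons are the stated focus of the primary models. In 2 v 3 and 3 v 4 the treated and untreated women come from different recruitment waves and were never candidates for the same allocation. If later recruits differ in knowledge, age, marital status or schooling, that difference goes into the apparent club effect. A reader who relies on the word randomised would give all three contrasts a protection that at most one has.

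**Working it through.** **1. Count destinations.** Inputs are from Section III, item 3a. Recruitment is 50 + 25 + 25 = 100, which matches the stated 100.

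| Group | Wave | n | Open at enrolment |
|---|---|---|---|
| 1 | 1 | 25 | club or wait-list |
| 2 | 1 | 25 | club or wait-list |
| 3 | 2 | 25 | wait-list only |
| 4 | 3 | 25 | wait-list only |

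Women who can be randomised: 25 + 25 = 50 of 100. Contrasts within one wave: only 1 v 2, so at most 1 of 3. The random selection of block sectors is sampling, not allocation, and no section randomises sectors, groups or start times. If each club belongs to one sector, the plan must still explain how two women in the same sector could be allocated to different clubs.

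**2. Survey timing, on the prose alone.** Assume clubs of 2.5 months run back to back (U untreated, T treated):

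| Group | First survey | Second survey |
|---|---|---|
| 1 | month 0, U | month 2.5, T |
| 2 | month 0, U | month 5, T |
| 3 | month 2.5, U | month 7.5, T |
| 4 | month 5, U | month 10, T |

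On this schedule each planned contrast compares surveys 2.5 months apart: 1T at 2.5 v 2U at 0; 2T at 5 v 3U at 2.5; 3T at 7.5 v 4U at 5.

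**3. What a model can estimate on that schedule.** Inputs: SD 3 and difference 1.3 (power paragraph), 25 per group, and an assumed within-woman correlation ρ. For the group means, V within a group = (9/25)[(1−ρ)I + ρJ], and Var(estimates) = (XᵀV⁻¹X)⁻¹.

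- *Categorical period plus fixed wave terms: not estimable.* Add any constant c to the club effect, +c to waves 2 and 3, −c to the effects of months 2.5 and 5, and −2c to those of months 7.5 and 10. Every expected mean is unchanged. For example, 1T at 2.5 changes by c − c = 0; 3U at 2.5 by c − c = 0; 3T at 7.5 by c + c − 2c = 0.
- *Linear time plus wave terms:* SE 1.28, 1.14 and 0.92 at ρ = 0.3, 0.5 and 0.7.
- *Categorical period, no wave terms:* the information comes from 1T v 3U at month 2.5 and 2T v 4U at month 5. Each difference has variance 2 × 9/25 = 0.72. Their average has variance 0.72/2 = 0.36, so SE = 0.60 at each of these ρ. This is valid only if waves are exchangeable.

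**4. Add one survey of group 2 at month 2.5, before its club.** Groups 1 and 2, from the same wave, can then be compared at the same time. With categorical period and wave terms, SE is 0.81, 0.74 and 0.61 at ρ = 0.3, 0.5 and 0.7. With group terms in place of wave terms it is 1.00, 0.85 and 0.66.

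**The case against.** The strongest reply is that the defect is one word. The Study Design paragraph and Section I, item 13 present a wait-listed, modified stepped-wedge design in which participants act as their own controls. The analysis paragraph speaks openly of recruitment cohorts. The stated hypotheses for Aims 2 and 3 are pre/post and need no randomised 2 v 3 or 3 v 4 contrast. This stands as far as it goes, and a reader should not infer that the sequential structure is hidden. It does not remove the point, because the cross-cohort models are primary and their randomised and non-randomised parts are not separated.

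Three stronger readings are tempting, and the documents do not support them.

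- *Group 2 has no untreated score when club 1 ends.* The prose lists none, but Figure 2 is missing here and may show one. The plan to use untreated group 2 participants may imply it. This is a point to clarify.
- *The 2 v 3 and 3 v 4 contrasts are confounded with calendar time in any case.* Lack of randomisation gives confounding with wave. Confounding with calendar time follows only if the compared surveys are not concurrent, which again depends on the schedule.
- *The club effect cannot be estimated.* That is true only without an end-of-wait survey for group 2 and with categorical period plus fixed wave (or group) terms, which the plan does not specify. Other models estimate it, at the price of stronger assumptions.

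**Conclusion.** The contradiction is real and should be corrected. At most 50 of 100 women and one of three between-group contrasts can be randomised. This follows from the recruitment text alone and needs no numerical assumption. Whether 1 v 2 is itself randomised stays open until allocation is reconciled with sector-based clubs. The other two contrasts are comparisons of successive recruitment waves and should be read as such.

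The consequence for the model is conditional. If no end-of-wait survey of group 2 exists, the analyst must choose among a model that cannot be fitted, an imprecise one (SE 1.14 at ρ = 0.5 against a planned difference of 1.3), and one that takes waves as exchangeable (SE 0.60). Random allocation of start times would have justified exchangeability; this recruitment sequence does not. These SEs assume SD 3, 25 per group with no loss, back-to-back 2.5-month clubs and common survey dates within a group. They show scale only, since item 3a itself allows for variable time to assemble groups.

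**What to change.** **Wording and analysis plan (no extra data):**

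- Reconcile the randomisation sentence in Section I, item 4 with Section III, items 3a and 3b.
- State that at most groups 1 and 2 are randomised, and how that allocation works with clubs held in separate sectors.
- Report 1 v 2 as the randomised contrast, and 2 v 3 and 3 v 4 as non-randomised.
- Say how recruitment wave and period enter the mixed model.

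**Survey schedule:** set out in the text when each group is surveyed. If group 2 is already surveyed at the end of its wait, the model with categorical period and wave terms can be fitted and nothing more is needed. If not, choose one of two courses:

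- Add that survey, before group 2 starts its club: about 25 on top of 100 × 2 = 200. SE is about 0.74 with wave terms at ρ = 0.5. The drawback is that group 2 meets the knowledge items three times, so some learning from repeat testing is possible.
- Keep the schedule and state openly that the estimate assumes exchangeable waves.

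The added survey makes only 1 v 2 concurrent. The other two contrasts would remain non-randomised whatever surveys were added. Sample size, number of clubs and study length do not change.

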Hypothesis Aim 1: Community engagement and mixed methods data will yield insights into current treatment seeking patterns and needs for AGYW and effective adaptation strategies to improve the proposed intervention.

Aim 2: Implement a pilot of the intervention and assess implementation outcomes.

The provider and staff component will consist of two groups to facilitate participation and accommodate provider/staff schedules. Four separate groups of AGYW will participate in the adolescent health club component, using a wait-list control group design. Separate groups are needed due to the group nature of the intervention activities which limits the number of people who can participate at one time. Intervention participants will be surveyed pre- and post-intervention to examine acceptability, feasibility, and uptake. Qualitative process data will also be collected and analyzed.

Hypothesis Aim 2: AGYW's satisfaction with services will improve 20% post-intervention compared to pre-intervention.

Aim 3: Assess a pilot set of health outcomes for future research.

Quantitative pre- and post-tests will also assess pilot effectiveness health and behavioral outcomes.

Hypothesis Aim 3: Sexual and reproductive health (SRH) knowledge will show statistically significant improvement post-intervention. Behavioral elements of SRH will show positive trends, but will not be statistically significant.

2. **Probable Duration of Project:** State the expected duration of the project, including all follow-up and data analysis activities.

5-6 years

3. **Background:** Describe the background information that led to the plan for this project. Provide references to support the expectation of obtaining useful scientific data.**A.1. Status of adolescent sexual and reproductive health (SRH) and adolescent-friendly health services**

Most of the over one billion people between the ages of 15-25 in the world live in low- and middle-income countries (LMICs). Among youth living in LMICs, 70% are in Asia.⁽¹⁾ Among health, education, and employment challenges facing young people, SRH need specific action.⁽²⁻⁷⁾ Adolescent girls and young women (AGYW) are particularly vulnerable with adolescent pregnancy, maternal morbidity and mortality, STIs/HIV, gender-based violence, and psychological trauma stemming from these issues given their precarious status in patriarchal cultures.⁽⁸⁻¹¹⁾ While striving to achieve the Millennium Development Goals, the global health agenda largely

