
Table 1: Domains to be covered in AGYW pre- and post-intervention surveys.

Pre-Intervention Survey Domains	Post-Intervention Survey Domains

Demographics	Demographics
Clinic service uptake/use	Clinic service uptake/use ^(32, 130)
SRHR knowledge	SRHR knowledge ^(123, 131)
Violence and safety	Violence and safety ^(124, 125)
Gender norms	Gender norms ^(48, 132)
Agency	Agency ^(66, 133)
Mental health	Mental health ⁽¹²⁶⁾
	Intervention acceptability ⁽¹²⁹⁾
	Satisfaction with intervention/services ⁽¹²⁸⁾
	Feasibility ⁽¹²⁸⁾

Intervention Power Calculation and Sample Size Considerations: Power calculations and sample size for the adolescent health club component are determined based on the SRH knowledge measure.⁽¹²³⁾ With 85% power, in a two-arm comparison design (similar to round one in Figure 2 above), and based on data from a previous intervention study⁽¹³¹⁾ in which the investigators found a pre/post intervention difference of 1.3 and a standard deviation of 3, we will need 50 pairs or 100 participants in the adolescent clubs total. Broken into four groups, I plan for each group to be 25 participants. As this calculation does not take into consideration within-group analysis, it is a ≈20% overestimate, which allows for 20% loss to follow-up, or participant drop-out without loss of statistical power. However, to minimize bias, I am targeting 95% follow-up. 95% follow-up is based on our team's procedures for tracking and retaining adolescent health club participants. Specifically, we will make clear the participation expectations upon recruitment, consent, and the initial health club meeting. We will follow-up with participants who miss club sessions via cell phone and home visits as needed. These methods have been used by the research team in previous studies in the study area.

Implementation and Intervention Data Analysis

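### The Aim 2 satisfaction hypothesis has no stated baseline, and the post-only Aim 2 scores may describe only women who finish the club

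*Combined protocol and SAP*

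**What the plan says.** **Satisfaction.** Section I.1 states the Aim 2 hypothesis as a change over time: young women's "satisfaction with services will improve 20% post-intervention compared to pre-intervention". Table 1 in Section I.4 sets out the survey domains in two columns. Seven domains, from demographics to mental health, appear in both. Three appear in the post-intervention column only: acceptability, satisfaction and feasibility. The satisfaction entry covers the intervention and services under one label.

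**Timing of the post-survey.** Two places schedule it. Section I.4 (Adolescent Health Club Component and Evaluation) says "When young women complete the curriculum, they will also complete the post-intervention evaluation instrument". Section III.3 (Recruitment Procedures) says "When young women complete the health club curriculum, they will also complete the post-intervention evaluation instrument". Neither states how much attendance counts as completing, gives a calendar window, or says what happens for a woman who stops coming.

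**Losses.** Section III.3 says "Factoring in an attrition rate of 20%, the expected N at endpoint is 80". The sample-size paragraph of Section I.4 also allows for 20% loss, then adds "However, to minimize bias, I am targeting 95% follow-up", to be reached partly as follows: "We will follow-up with participants who miss club sessions via cell phone and home visits as needed". The post-survey is not mentioned among those steps.

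**Text pointing the other way.** Section I.1 says "Intervention participants will be surveyed pre- and post-intervention to examine acceptability, feasibility, and uptake", and the quantitative analysis paragraph of Section I.4 expects before-and-after measurements on every subject.

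**The concern.** A pre-to-post improvement needs a pre-intervention value of the same quantity. Satisfaction with the club cannot have one, but satisfaction with services can, and it is the latter that the hypothesis names. If it is not asked at enrolment, the one numerical hypothesis of Aim 2 cannot be tested as stated.

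The timing rule affects the same outcomes. Acceptability and feasibility are what Aim 2 sets out to examine, and like satisfaction they are measured once. If the survey reaches only women who finish, the scores describe women who stayed. A repeated-measures model does not help, because a leaver has no earlier value on these scales. Weighting or imputation from the seven baseline domains could help under a missing-at-random assumption, but the plan specifies neither.

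**Working it through.** **1. Satisfaction: hypothesis against survey content.** The hypothesis needs satisfaction with services at two times. Table 1 gives it at one. The nearest domain measured at both times is clinic service uptake and use. It may hold related items, but the plan does not say so and names no item as the baseline for the 20% improvement.

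**2. Which reading of completion applies?**
- *End of the group's round.* Section III.3 also uses the word for whole groups: the next group starts once the first has completed. The Aim 2 text and the quantitative analysis paragraph fit this reading.
- *The individual woman finishing.* This is the literal sense of the two scheduling sentences, whose subject is young women. Section III.3 speaks of four groups of 20 to 25 completing and then gives 80 at endpoint. Since 4 × 20 = 80, that is consistent with the endpoint count being a count of finishers, though attrition is never defined that way.

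The text does not settle it, and field staff could follow either.

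**3. How many women.** Planned enrolment is 100 (Section III.1).
- Plan's endpoint figure: 100 × (1 − 0.20) = 80, which reproduces.
- At the follow-up target: 100 × 0.95 = 95.

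So at most 20 or at most 5 women lack a post-survey because of the trigger. These are ceilings. They equate attrition with not finishing, whereas Section I.4 counts loss to follow-up and drop-out together. Women who cannot be reached, or who withdraw consent, are missing under any trigger.

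**4. Effect on a mean score.** Let L be the share not surveyed and d the difference between finishers and leavers in SD units. The finishers' mean differs from the mean for all enrolled by L × d. The standard error is 1/√n in SD units. Assumed d: 0.25 to 0.5.

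| L | n | Shift (SD) | Standard error (SD) | Shift / SE |
|---|---|---|---|---|
| 0.20 | 80 | 0.05 to 0.10 | 0.112 | 0.45 to 0.89 |
| 0.05 | 95 | 0.0125 to 0.025 | 0.103 | 0.12 to 0.24 |

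At 20% loss the shift stays under half the 95% half-width (1.96 × 0.112 = 0.22 SD). At 5% it is negligible.

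**5. Outer limits for a proportion.** The plan defines no proportion finding the club acceptable, so the observed share p is assumed to be 70% to 90%. If none or all of the unsurveyed women find it acceptable, the value for all enrolled lies between p(1 − L) and p(1 − L) + L. The sampling 95% interval has width 2 × 1.96 × √(p(1 − p)/n).

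| p | L = 0.20: range | Sampling width (n = 80) | L = 0.05: range | Sampling width (n = 95) |
|---|---|---|---|---|
| 70% | 56 to 76% | 20.1 points | 66.5 to 71.5% | 18.4 points |
| 80% | 64 to 84% | 17.5 points | 76 to 81% | 16.1 points |
| 90% | 72 to 92% | 13.1 points | 85.5 to 90.5% | 12.1 points |

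The 20-point range reflects all-or-none behaviour among leavers and is an extreme, not an expected error.

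**The case against.** The best case for the plan is that completion means the end of a group's round, so everyone is surveyed then and only the wording is loose. The group-level usage in Section III.3 and the analysis text support this. It stands as a possible reading. It does not close the gap, because the analysis text describes the data expected and gives no procedure for a woman who has stopped attending.

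Second, the plan has other sources on leavers. Session logs record unusual events and "the effect of these events on implementation, acceptability, or feasibility", fieldnotes and a focus group address acceptability, and the monitoring committee (Section I.12) reviews how many women drop out and why. These give useful context, but none supplies a leaver's score, and the focus group is not said to include leavers.

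Third, contact details. Section IV.1 destroys phone and email details once participation in the intervention is completed. A reader might infer that leavers become unreachable. The documents do not establish that: Section IV.5 ties destruction to the end of study activities or a request, and women are identified through households, so a home visit need not depend on a phone number. The two sections should be aligned, but they do not flatly contradict each other.

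Fourth, the uptake domain may already contain satisfaction items. That is possible, so it goes too far to say that no baseline will exist. What can be said is that none is stated.

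**Conclusion.** Two points hold. The firmer is that the Aim 2 hypothesis compares satisfaction with services after and before the intervention, while the plan's own domain list places satisfaction after only. As written, the hypothesis has no stated baseline.

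The second is conditional. On the literal reading, women who stop attending are not surveyed, and the three post-only scores describe those who stayed. A reader might infer that 20 women will certainly be lost this way, or that the resulting bias matches sampling error. The documents support neither. The 20 is a ceiling that mixes several kinds of loss. The direction of bias is unknown, since some women may leave because of the club and others for unrelated reasons such as restricted mobility. Only the all-or-none bounds on a proportion, at 20% loss, are about as wide as the sampling interval or wider. With assumed differences of 0.25 to 0.5 SD, a mean shifts by 0.45 to 0.89 of a standard error at 20% loss, and the issue is small if the 95% target is met.

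**What to change.** **Satisfaction.** Add the satisfaction-with-services items to the pre-survey, or name the baseline items in the existing uptake domain that will serve. Failing both, restate the Aim 2 hypothesis as a post-only estimate.

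**Timing.** In Section I.4 and Section III.3:
- Offer the post-survey at the end of each group's roughly 2.5-month round to every enrolled woman who has not withdrawn consent, whatever her attendance, using the calls and home visits already planned.
- Analyse by assigned group, and report scores by sessions attended, with an unable-to-rate option, since women who came to few sessions may not be able to answer some items.
- State how post-only scores that are still missing will be handled.

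**Contact details.** Align Sections IV.1 and IV.5 so that details are kept until that survey is done, unless the woman asks for deletion.

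**Cost.** The pre-survey becomes slightly longer for all 100 women. There are at most about 5 to 20 extra surveys (25 × 0.05 = 1.25 to 25 × 0.20 = 5 per group), some of which will not be obtained. Each may need a home visit, a private space and the 48-hour review of survey data in Section IV.1. Section VI.2 pays per session attended, so payment for a survey without a session must be specified. At the same 200 rupees (about 2.80 USD; assumption) the ceiling is 20 × 2.80 = 56 USD. If the end-of-round reading was always intended, the timing change is mainly wording.
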